91 largely been ignored by the literature. Due to the magnitude of the problem of obesity,
92 and the potential benefits of exercise with this population, it is important to determine the
93 elements of a feasible and effective physical activity program.

94

95 **SPECIFIC AIMS AND SCOPE OF THE PROPOSED RESEARCH**

96 The proposed research is a collaborative study involving the Eastern Maine Medical
97 Center Weight Management Program. This program currently has no formal physical
98 activity recommendation for its non-surgical participants. The Weight Management
99 Program managers are seeking guidance as to successful physical activity
100 recommendations for their patients. It is anticipated that a wide demographic will be
101 represented allowing the results to be applied across the spectrum of age and gender.

102 Objectives:

103 1. Identify any difference in the functional outcome measures resulting from
104 participation in the different forms of physical activity

105 2. Identify differences in compliance among the various types of physical activity with
106 the supervised group and individual sessions.
107 3. Determine the impact of the type of physical activity on the health measures
108 collected including blood pressure, and weight.
109 4. Identify differences in self-reported quality of life measures resulting from
110 participation in the different physical activities.

111

112

113 Clearly, an intervention that would reduce mobility deficits in this population and
114 improve overall health could have a tremendous impact on quality of life for a large
115 portion of the population. The overarching aim of the proposed study is thus to help
116 identify a beneficial and feasible program to impact activity level and therefore health
117 and well-being of people with morbid obesity.

118 **PARTICIPANT RECRUITMENT AND SELECTION:** Participants will be recruited from the Eastern
119 Maine Medical Center Weight Management practice in Bangor, Maine. The anticipated number
120 of participants will be 45 with 15 participants in each of 3 groups. Adult clients will be included
121 if they are at least 21 years old with no restriction on upper age range. Male and female clients
122 will both be included. Inclusion criteria are as follows: Body mass index (BMI) greater than 40,
123 as determined by the physician's office, and successful performance on the Four Square Step

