150 doing resistance training along with another control group. After each intervention phase (Tai
151 chi or resistance training), a shorter, 4-week intervention program will be offered to those
152 people who have participated in the control group. This will serve as a reward for participation,
153 and will also encourage people to return for measurements. Thus it should take approximately
154 21 months to complete the entire study. We understand that we will need to apply for an
155 extension of the protocol after the first year of progress on this study.

156 **RESEARCH DESIGN:** This pilot study will compare three different approaches to provision of
157 physical activity with morbidly obese participants in a Weight Management Program. The
158 participants will be recruited through Eastern Maine Weight Management Program using flyers
159 and pamphlets (See page 28 for an example of the flyer). If they meet the pre-screening
160 minimum requirement for safe dynamic standing balance, they will be eligible to complete the
161 initial outcome measures at that time, and to participate in the rest of the program.

162 In order to allow the researchers to feasibly carry out this study, it will be completed over two
163 academic years. During the first year, data will be collected for the control group and for one of
164 the intervention groups (Tai Chi). The following year, data will be collected for the other
165 intervention group (resistance exercise) and an additional control group. This is a repeated
166 measures study with measures being taken just prior to the initiation of the exercise program
167 and then again after the conclusion of 8 weeks of interventions. The use of control groups for
168 both phases will allow researchers to be blinded to group assignment as they take the pre-and
169 post-test measurements.

170 After providing informed consent, each potential participant will first be asked to perform the
171 Four Square Step Test (FSST) to determine eligibility for admission to the study. This test will
172 identify those at risk for falls, and they will be excluded from the rest of the study. For this test,
173 participants begin by standing in one quadrant of a square formed by one-inch PVC pipes
174 secured together with a cross connector placed on the floor forming a grid (Figures 1 and 2).
175 They are asked to step in a specific sequence through each of the quadrants of the square. A

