202 rises is recorded. Lastly, the researchers will ask the participants to walk down a Zeno walkway,
203 which is an instrumented 20-foot pad that records gait parameters electronically. The

204 researchers performing the outcome measures data collection will be blinded to the group
205 assignment of the participants.

206 The groups of participants will include two intervention groups and two corresponding control
207 groups. The control groups will receive the instruction in participation in physical activity
208 currently provided by the Weight Management Program, but will receive no formal interaction
209 with an exercise instructor or physical therapist during the study period. This is the current
210 standard protocol, so no treatment is being withheld from this group of participants. One
211 intervention group will be instructed in Tai Chi exercises during weekly supervised exercise
212 sessions. A commercially available DVD will be utilized to lead the exercise session with close
213 supervision of technique and safety by the assigned researchers. Participants in this group will
214 be provided with an identical Tai Chi DVD to use during their home sessions. The DVD was
215 created by [name], a Tai Chi master who is also a medical doctor, and is specifically geared
216 towards people with arthritis who want to enjoy Tai Chi. We chose this because we could not
217 find a DVD that had been developed for people with obesity, and since many obese people
218 would also benefit from joint protection techniques, we felt that the modifications the master
219 has made for this population would be appropriate for our targeted research participants.

220 Following completion of the 8-week study period, the people who were assigned to the
221 corresponding control group will be offered a 4-week supervised Tai Chi program along with the
222 accompanying DVD. We hope that this will help provide an incentive for them to return for the
223 second measurement session, and will also reward them for participating as part of the control
224 group.

225 In the second phase of the study, a group will be instructed in an exercise program of resisted
226 exercises for trunk, upper and lower extremities and stretching exercises. These participants
227 will attend one supervised session per week and will have a DVD to use at home to remind them

228 of the exercises. This DVD will be created and produced by the researchers specifically for this

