306 this study may provide guidance towards improving mobility and health in people who are
307 morbidly obese.

308 **DATA COLLECTION:** Measurements will be taken on one session prior to, and on one session
309 following completion of the 8 weeks of exercise sessions. A sample data collection form is found
310 on page 31. The participant identification numbers will be the only identifying information
311 utilized during data collection and analysis. Records of the identification codes for the
312 participants will be kept by the primary investigators only, and will be stored in hard copy in
313 their locked offices, and on their password-protected computers. These codes will be stored in
314 a separate file from the research data, so that if there were a breach of the computer, the
315 identity codes would not be obvious. Any data created and collected on paper by this study will
316 be kept in the locked offices of the primary investigators. The paper data will be transferred to
317 spreadsheets on the computers of the primary investigators, which are password
318 protected. When the data are transferred to the electronic spreadsheets, only the numerical
319 codes will be used, so even if there were a breach of the computer, individual identities would
320 not be revealed. The researchers who are assigned to collect pre-test and post-test outcome

321 measures will be excluded from participation in the exercise class instruction for all groups in
322 order to maintain blinding of the researchers. The data will be analyzed using SPSS software.
323 Analysis of the test results among the test groups will include repeated measures ANOVA to
324 compare performance on the outcome measures from initiation of the exercise program to the
325 conclusion.

326 **FUNDING:** A small internal grant from Husson University will cover the cost of the DVDs and the
327 resistance equipment required for the resistance training group. No additional funding will be
328 necessary. The exercise sessions will be monitored by students who are receiving course credit
329 and therefore do not receive reimbursement for their time, and the faculty members who will
330 be present are required to carry out this research as part of their teaching loads.

331 CONSENT FORM: See attached Informed Consent Form. This form has a Fleish-Kincaid
332 readability level of 9.0. All researchers will be instructed as to how to properly administer an

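### Outcomes measured once before and once after are to be compared by repeated measures ANOVA; a model adjusted for the pre-test would usually be more precise, and the term that answers the between-group objectives is not named

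*Combined protocol and SAP*

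**What the plan says.** The analysis plan is the end of the DATA COLLECTION section. After naming SPSS it says: "Analysis of the test results among the test groups will include repeated measures ANOVA to" "compare performance on the outcome measures from initiation of the exercise program to the" end of the programme. No covariate, model term, between-group estimate, confidence interval or significance level is given.

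There are two time points. RESEARCH DESIGN describes a repeated "measures study with measures being taken just prior to the initiation of the exercise program" and again after eight weeks. DATA COLLECTION agrees: "Measurements will be taken on one session prior to, and on one session" after it. The data collection forms list the same outcomes at both visits.

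Objectives 1, 3 and 4, under SPECIFIC AIMS AND SCOPE, ask about differences between, or the impact of, types of activity.

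On group sizes, PARTICIPANT RECRUITMENT AND SELECTION expects that the number "of participants will be 45 with 15 participants in each of 3 groups". RESEARCH DESIGN says: "The groups of participants will include two intervention groups and two corresponding control" groups, one pair per phase. On allocation, the same section says: "Following completion of the 8-week study period, the people who were assigned to the" control group are later offered a short programme. The text available for review does not say how that assignment is made.

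**The concern.** A repeated measures ANOVA with two visits yields three tests: time, group, and group-by-time. Only group-by-time asks whether the groups changed differently, and with two visits it is a t-test on change scores. That subtracts the whole pre-test value, whatever its actual relation to the post-test. A model that estimates the relation uses the same data and is usually more precise, and with about 15 people per group precision is scarce.

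The choice of term also matters. Everyone is told to walk daily and everyone repeats the same performance tests, so a time effect can appear in all groups without any effect of Tai Chi or resistance exercise. The group main effect averages in the pre-test, where no treatment effect can exist, and so dilutes a real difference. Without a named term, one output table can support quite different conclusions.

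**Working it through.** **The plan's own figure.** 3 × 15 = 45 is consistent as arithmetic. No power, effect size, SD, alpha or correlation stands behind it, so there is no sample-size calculation to reproduce.

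**Inputs.** From the document: two visits; 15 per group. The size of each phase's control group is not stated. Two controls of 15 plus two interventions of 15 would be 60, which exceeds 45. If 15 controls are split over the phases, each has 7 or 8. I therefore use 15 v 15, 15 v 8 and 15 v 7. Assumed: two-sided 5%, SD of 1 at both visits, pre-post correlation r from 0.5 to 0.98, and no systematic baseline difference for the precision comparison.

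**Formulas.** The residual variance is 2(1 − r) for change scores and 1 − r² for the adjusted model. Their large-sample ratio is 2/(1 + r). With N = n₁ + n₂, the expected 95% half-widths are:

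- change score: t(N − 2) × √[2(1 − r)(1/n₁ + 1/n₂)]
- adjusted: t(N − 3) × √[(1 − r²)(1/n₁ + 1/n₂)(1 + 1/(N − 4))]

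The last factor allows for chance baseline imbalance.

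Example, 15 v 15, r = 0.7:
- change score: 2.048 × √(0.60 × 0.1333) = 0.579
- adjusted: 2.052 × √(0.51 × 0.1333 × 1.0385) = 0.545
- ratio: 1.06

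| r | 15 v 15: change / adjusted (SD) | Ratio | 15 v 8 ratio | 15 v 7 ratio |
|---|---|---|---|---|
| 0.5 | 0.748 / 0.661 | 1.13 | 1.12 | 1.12 |
| 0.7 | 0.579 / 0.545 | 1.06 | 1.05 | 1.05 |
| 0.8 | 0.473 / 0.458 | 1.03 | 1.02 | 1.02 |
| 0.9 | 0.335 / 0.333 | 1.005 | 0.997 | 0.995 |
| 0.95 | 0.237 / 0.238 | 0.992 | 0.984 | 0.982 |
| 0.98 | 0.150 / 0.152 | 0.985 | 0.977 | 0.975 |

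The methods break even at r of about 0.92 (15 v 15), 0.89 (15 v 8) and 0.88 (15 v 7).

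**Which term is read.** In 20,000 simulated trials of 15 v 15 with a true difference of 0.8 SD and r = 0.7, the rejection rates were 78% for group-by-time, 83% for the adjusted group term and 21% for the group main effect.

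For the time effect, suppose that everyone improves by 0.3 SD, no group differs and r = 0.7. The noncentrality is 0.3 × √n / √0.6:
- n = 45, both phases pooled: 2.60, significant about 72% of the time
- n = 30, one phase at 15 v 15: 2.12, about 54%
- n = 22, one phase at 15 v 7: 1.82, about 41%

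**If assignment is not random.** Take a true baseline difference of 0.5 SD, no treatment effect and r = 0.7.
- If the difference persists, the adjusted model gives 0.5 − 0.7 × 0.5 = +0.15 SD and the change score gives 0.
- If it regresses to 0.7 × 0.5 = 0.35, the change score gives 0.35 − 0.5 = −0.15 SD and the adjusted model gives 0.

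The two methods then estimate different quantities, and which one is unbiased depends on something that the data do not show.

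**The case against.** The strongest reply is that group-by-time is a valid test of difference in change, and that in a self-described pilot with no power target a 3% to 6% difference in interval width (r of 0.7 to 0.8) is modest. That stands: this is an improvement in precision, not the repair of an invalid test.

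A reader might infer that the planned method always gives wider intervals. The documents do not support that. They state no correlation, and above about 0.9 the gain disappears and slightly reverses. Weight and BMI over eight weeks could plausibly lie there, though that too is an assumption.

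A reader might also infer that the investigators mean to present the time effect as the result. The sentence speaks of comparison among the groups, and Objectives 1, 3 and 4 point the same way, so a between-group comparison of change is the natural reading. What remains is that the term is not named. The verb in the sentence also leaves room for other analyses, although none is listed.

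Finally, the case for adjustment is cleanest when groups are randomised. The text says only that people were assigned. It does not show that assignment was non-random, but it does not allow the adjusted model to be called better without qualification. This objection stands in full and shapes the fix.

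**Conclusion.** The point holds in a conditional form, as a change that should be made. At assumed correlations of 0.5 to 0.8 the planned comparison costs about 13% to 3% in interval width at 15 v 15, or 12% to 2% at 15 v 7. At about 0.9 it costs nothing, and above that the adjusted model is the wider by about 1% to 2.5%. These figures assume equal SDs at both visits and no systematic baseline difference.

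The unnamed term is a secondary gap that exists whatever the correlation. Its consequence could be larger than the loss of precision if the wrong row of the table were read, but the wording does not show that this is intended.

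**What to change.** Replace the analysis sentence with wording to this effect. For each outcome, within each phase and against that phase's concurrent control, the post-test value is modelled on group and pre-test value. The adjusted group difference with its 95% confidence interval is the result, and the time effect is descriptive only.

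State how participants are assigned to groups, and reconcile three groups of 15 with two intervention and two control groups. Because randomisation is not described, report the change-score (group-by-time) difference with its 95% interval next to the adjusted one, and treat a disagreement between the two as a sign of baseline imbalance.

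No new data are needed and SPSS fits the model. The cost is one degree of freedom, one extra reported line per outcome, and no gain in precision for outcomes with a correlation above about 0.9.

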526
527 If yes, please describe
528 _____
529 _____
530
531
532 5. What prescription medications are you taking?
533
534
535
536 6. Do you use an assistive device such as a walker or a cane to help you while
537 walking?
538
539
540
541
542

543 7. How many falls have you had in the past year, approximately? _____

544

545

546 When did those falls occur? _____

547

548

549 8. How long does it take you to get from you home to Husson? _____

550

551

552

553 9. What is your primary reason for participating in this study? _____

554

555 _____

556

557

558 10. What is your occupation? _____

559

560

561

562 11. How many hours per week do you work? _____

563

564

565

566

567

568
569**Data Collection Form:**

| | Pretest |
|---|---------|
| Participant ID number: | |
| Anthropometric Data: | |
| Height | |
| Weight | |
| BMI | |
| Neck Circumference | |
| Physical Outcome Measures: | |
| FSST (Time) | |
| 6 Minute Walk test | |
| Blood Pressure | |
| Heart Rate | |
| Distance | |
| 30 Sec Sit to Stand (#) | |
| TUG Score (time) | |
| Gait Measures | |
| Gait speed | |
| Step length | |
| Step width | |
| Double limb support time | |
| Cadence | |
| Paper and pencil surveys | |
| SF-36 Score | |
| Rapid Assessment of Phys Activ | |
| Number of sessions attended at Husson | |
| Number of times exercised independently | |

570
571

572

Data Collection Form:

573

| | Post test |
|---|-----------|
| Participant ID number: | |
| Anthropometric Data: | |
| Height | |
| Weight | |
| BMI | |
| Neck Circumference | |
| Physical Outcome Measures: | |
| FSST (Time) | |
| 6 Minute Walk test | |
| Blood Pressure | |
| Heart Rate | |
| Distance | |
| 30 Sec Sit to Stand (#) | |
| TUG Score (time) | |
| Gait Measures | |
| Gait speed | |
| Step length | |
| Step width | |
| Double limb support time | |
| Cadence | |
| Paper and pencil surveys | |
| SF-36 Score | |
| Rapid Assessment of Phys Activ | |
| Number of sessions attended at Husson | |
| Number of times exercised independently | |

574

575
